4. STUDY PROCEDURES AND SCHEDULE OF EVENTS

[figure not shown]
4.1 Schedule of Events

4.2 Observations of Curative Effects

The following symptoms should be observed and documented for evaluation:

4.3 Scoring of Clinical Symptoms

4.3.1 Severity of local signs - Phenotypes

a) Induration (elevation)

The NPF induration card is to be used to assist the induration assessments.

Table 1 Induration (average over all lesions)

[figure not shown]
b) Erythema (Redness)

Table 2 Erythema (average over all lesions)

[figure not shown]
3	Moderate	reddish patchy coloration
4	Severe	bright red coloration
5	Very severe	dusky to deep red coloration

c) Scaling

Table 3 Scaling (average over all lesions)

4.3.2 Extent - Body Surface Area (BSA) Affected

1. *Journal of the American Medical Association*, 277: 1025-1030, 1997.

4.3.3 Symptoms - Pruritus (Itching)

the 1990s, the number of people in the United States who are 65 years of age or older has increased by 50 percent, and the number of people 75 years of age or older has increased by 100 percent. The number of people 85 years of age or older has increased by 200 percent. The number of people 90 years of age or older has increased by 400 percent. The number of people 95 years of age or older has increased by 800 percent. The number of people 100 years of age or older has increased by 1,600 percent. The number of people 105 years of age or older has increased by 3,200 percent. The number of people 110 years of age or older has increased by 6,400 percent. The number of people 115 years of age or older has increased by 12,800 percent. The number of people 120 years of age or older has increased by 25,600 percent. The number of people 125 years of age or older has increased by 51,200 percent. The number of people 130 years of age or older has increased by 102,400 percent. The number of people 135 years of age or older has increased by 204,800 percent. The number of people 140 years of age or older has increased by 409,600 percent. The number of people 145 years of age or older has increased by 819,200 percent. The number of people 150 years of age or older has increased by 1,638,400 percent. The number of people 155 years of age or older has increased by 3,276,800 percent. The number of people 160 years of age or older has increased by 6,553,600 percent. The number of people 165 years of age or older has increased by 13,107,200 percent. The number of people 170 years of age or older has increased by 26,214,400 percent. The number of people 175 years of age or older has increased by 52,428,800 percent. The number of people 180 years of age or older has increased by 104,857,600 percent. The number of people 185 years of age or older has increased by 209,715,200 percent. The number of people 190 years of age or older has increased by 419,430,400 percent. The number of people 195 years of age or older has increased by 838,860,800 percent. The number of people 200 years of age or older has increased by 1,677,721,600 percent. The number of people 205 years of age or older has increased by 3,355,443,200 percent. The number of people 210 years of age or older has increased by 6,710,886,400 percent. The number of people 215 years of age or older has increased by 13,421,772,800 percent. The number of people 220 years of age or older has increased by 26,843,545,600 percent. The number of people 225 years of age or older has increased by 53,687,091,200 percent. The number of people 230 years of age or older has increased by 107,374,182,400 percent. The number of people 235 years of age or older has increased by 214,748,364,800 percent. The number of people 240 years of age or older has increased by 429,496,729,600 percent. The number of people 245 years of age or older has increased by 858,993,459,200 percent. The number of people 250 years of age or older has increased by 1,717,986,918,400 percent. The number of people 255 years of age or older has increased by 3,435,973,836,800 percent. The number of people 260 years of age or older has increased by 6,871,947,673,600 percent. The number of people 265 years of age or older has increased by 13,743,895,347,200 percent. The number of people 270 years of age or older has increased by 27,487,790,694,400 percent. The number of people 275 years of age or older has increased by 54,975,581,388,800 percent. The number of people 280 years of age or older has increased by 109,951,162,777,600 percent. The number of people 285 years of age or older has increased by 219,902,325,555,200 percent. The number of people 290 years of age or older has increased by 439,804,651,110,400 percent. The number of people 295 years of age or older has increased by 879,609,302,220,800 percent. The number of people 300 years of age or older has increased by 1,759,218,604,441,600 percent. The number of people 305 years of age or older has increased by 3,518,437,208,883,200 percent. The number of people 310 years of age or older has increased by 7,036,874,417,766,400 percent. The number of people 315 years of age or older has increased by 14,073,748,835,532,800 percent. The number of people 320 years of age or older has increased by 28,147,497,671,065,600 percent. The number of people 325 years of age or older has increased by 56,294,995,342,131,200 percent. The number of people 330 years of age or older has increased by 112,589,990,684,262,400 percent. The number of people 335 years of age or older has increased by 225,179,981,368,524,800 percent. The number of people 340 years of age or older has increased by 450,359,962,737,049,600 percent. The number of people 345 years of age or older has increased by 900,719,925,474,099,200 percent. The number of people 350 years of age or older has increased by 1,801,439,850,948,198,400 percent. The number of people 355 years of age or older has increased by 3,602,879,701,896,396,800 percent. The number of people 360 years of age or older has increased by 7,205,759,403,792,793,600 percent. The number of people 365 years of age or older has increased by 14,411,518,807,585,587,200 percent. The number of people 370 years of age or older has increased by 28,823,037,615,171,174,400 percent. The number of people 375 years of age or older has increased by 57,646,075,230,342,348,800 percent. The number of people 380 years of age or older has increased by 115,292,150,460,684,697,600 percent. The number of people 385 years of age or older has increased by 230,584,300,921,369,395,200 percent. The number of people 390 years of age or older has increased by 461,168,601,842,738,790,400 percent. The number of people 395 years of age or older has increased by 922,337,203,685,477,580,800 percent. The number of people 400 years of age or older has increased by 1,844,674,407,370,955,161,600 percent. The number of people 405 years of age or older has increased by 3,689,348,814,741,910,323,200 percent. The number of people 410 years of age or older has increased by 7,378,697,629,483,820,646,400 percent. The number of people 415 years of age or older has increased by 14,757,395,258,967,641,292,800 percent. The number of people 420 years of age or older has increased by 29,514,790,517,935,282,585,600 percent. The number of people 425 years of age or older has increased by 59,029,581,035,870,565,171,200 percent. The number of people 430 years of age or older has increased by 118,059,162,071,741,130,342,400 percent. The number of people 435 years of age or older has increased by 236,118,324,143,482,260,684,800 percent. The number of people 440 years of age or older has increased by 472,236,648,286,964,521,369,600 percent. The number of people 445 years of age or older has increased by 944,473,296,573,929,042,739,200 percent. The number of people 450 years of age or older has increased by 1,888,946,593,147,858,085,478,400 percent. The number of people 455 years of age or older has increased by 3,777,893,186,295,716,170,956,800 percent. The number of people 460 years of age or older has increased by 7,555,786,372,591,432,341,913,600 percent. The number of people 465 years of age or older has increased by 15,111,572,745,182,864,683,827,200 percent. The number of people 470 years of age or older has increased by 30,223,145,490,365,729,367,654,400 percent. The number of people 475 years of age or older has increased by 60,446,290,980,731,458,735,308,800 percent. The number of people 480 years of age or older has increased by 120,892,581,961,462,917,470,617,600 percent. The number of people 485 years of age or older has increased by 241,785,163,922,925,834,941,235,200 percent. The number of people 490 years of age or older has increased by 483,570,327,845,851,669,882,470,400 percent. The number of people 495 years of age or older has increased by 967,140,655,691,703,339,764,940,800 percent. The number of people 500 years of age or older has increased by 1,934,281,311,383,406,679,529,881,600 percent. The number of people 505 years of age or older has increased by 3,868,562,622,766,813,359,059,763,200 percent. The number of people 510 years of age or older has increased by 7,737,125,245,533,626,718,119,526,400 percent. The number of people 515 years of age or older has increased by 15,474,250,491,067,253,436,239,052,800 percent. The number of people 520 years of age or older has increased by 30,948,500,982,134,506,872,478,105,600 percent. The number of people 525 years of age or older has increased by 61,897,001,964,269,013,744,956,211,200 percent. The number of people 530 years of age or older has increased by 123,794,003,928,538,027,489,912,422,400 percent. The number of people 535 years of age or older has increased by 247,588,007,857,076,054,979,824,844,800 percent. The number of people 540 years of age or older has increased by 495,176,015,714,152,109,959,649,689,600 percent. The number of people 545 years of age or older has increased by 990,352,031,428,304,219,919,299,379,200 percent. The number of people 550 years of age or older has increased by 1,980,704,062,856,608,439,838,598,758,400 percent. The number of people 555 years of age or older has increased by 3,961,408,125,713,216,879,677,197,516,800 percent. The number of people 560 years of age or older has increased by 7,922,816,251,426,433,759,354,395,033,600 percent. The number of people 565 years of age or older has increased by 15,845,632,502,852,867,518,708,790,067,200 percent. The number of people 570

5. MEASUREMENT OF EFFECT

5.1 Clinical End Points

Clinical outcomes will be evaluated by following the criteria:

1. Primary Endpoint:
 - (1) Investigator's Static Global Assessment (ISGA)
 - (2) Assessment of Target Lesions
2. Secondary Endpoint:
 - (1) PASI \geq 75% improvement
3. Tertiary Endpoint:
 - (1) Psoriasis Disability Index (PDI)
 - (2) Dermatology Life Quality Index (DLQI).

For the purposes of this study, patients should be evaluated at baseline (0) and reevaluated for response at 2, 4, 6, and 8 weeks. In addition, a rebound evaluation should also be obtained 4 weeks after the final evaluation of week 8.

The efficacy evaluation of all outcomes will be static ordinal, integer-valued, and scaled (e.g., success or failure), where 'success' involves a score of Clear/Almost Clear and a 2-grade improvement.

5.1.1 Investigator's Static Global Assessment (ISGA) Scale Definition

Table 6 Investigator's Static Global Assessment (ISGA) Scale Definition

Score	Grade	Definition
0	None	No plaque elevation above normal skin level; may have residual non-erythematous discoloration; no psoriatic scale; no itching. Plaque elevation = 0 (no elevation over normal skin) Scaling = 0 (no scale) Erythema = \pm (hyperpigmentation, pigmented macules, diffuse faint pink or red coloration)
1	Minimal	Essentially flat with possible trace elevation; faint erythema; no psoriatic scale Plaque elevation = \pm (possible but difficult to ascertain whether there is a slight elevation above normal skin) Scaling = \pm (surface dryness with some white coloration) Erythema = up to moderate (up to definite red coloration) Majority of lesions have individual scores for induration, erythema, scaling, BSA and Pruritus (as described above) that average 1.
2	Mild	Slight plaque elevation, scaling, and/or erythema. Plaque elevation = slight (slight but definite elevation, typically edges are indistinct or sloped) Scaling = fine (fine scale partially or mostly covering lesions) Erythema = up to moderate (up to definite red coloration) Majority of lesions have individual scores for induration, erythema, scaling,

		BSA and Pruritus (as described above) that average 2.
3	Moderate	Moderate plaque elevation, scaling, and/or erythema. Plaque elevation = moderate (moderate elevation with rough or sloped edges) Scaling = coarser (coarse scale covering most of all of the lesions) Erythema = moderate (definite red coloration) Majority of lesions have individual scores for induration, erythema, scaling, BSA and Pruritus (as described above) that average 3.
4	Severe	Marked plaque elevation, scaling, and/or erythema. Plaque elevation = marked (marked elevation typically with hard or sharp edges) Scaling = coarse (coarse, non-tenacious scale predominates covering most or all of the lesions) Erythema = severe (very bright red coloration) Majority of lesions have individual scores for induration, erythema, scaling, BSA and Pruritus (as described above) that average 4.
5	Very Severe	Very marked plaque elevation, scaling, and/or erythema. Plaque elevation = very marked (very marked elevation typically with hard sharp edges) Scaling = very coarse (coarse, thick tenacious scale over most of all of the lesions; rough surface) Erythema = very severe (extreme red coloration; dusky to deep red coloration) Majority of lesions have individual scores for induration, erythema, scaling, BSA and Pruritus (as described above) that average 5.

Efficacy Evaluation:

Success = [Baseline (ISGA ≥ 2) – follow-up ISGA score] ≥ 2 , meaning:

- Patients with “mild” psoriasis become “clear”.
- Patients with “moderate” psoriasis become “clear” or “almost clear”.
- Patients with “severe” psoriasis become at least “mild”, if not “clear” or “almost clear”.
- Patients with “very severe” psoriasis become at least “moderate” if not mild to clear.

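### ISGA grade 1 states two different erythema limits, so a flat, non-scaling lesion that stays definitely red can be a success or a failure from baseline grade 3

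*Combined protocol and SAP*

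**What the plan says.** Section 5.1 of the combined protocol and SAP lists the ISGA and the assessment of target lesions as the primary endpoints. Table 6 in section 5.1.1 defines each ISGA grade by a headline, then separate lines for plaque elevation, scaling and erythema. From grade 1 upward it adds a sentence that five component scores (induration, erythema, scaling, BSA, pruritus) average the grade number.

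The grade 1 headline is "Essentially flat with possible trace elevation; faint erythema; no psoriatic scale". The erythema line beneath it is "Erythema = up to moderate (up to definite red coloration", and the grade 2 row carries the same line. Grade 3 has "Erythema = moderate (definite red coloration". The grade 2 headline is "Slight plaque elevation, scaling, and/or erythema"; grade 3 uses the same construction with moderate in place of slight.

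Success is worded twice. Section 5.1.1 asks for a fall of at least 2 grades and spells out that a moderate patient must become clear or almost clear. Section 5.1 has "where 'success' involves a score of Clear/Almost Clear and a 2-grade improvement". Both require a patient with baseline grade 3 to reach 0 or 1.

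**The concern.** Faint and definitely red are different levels of erythema, and grade 1 names both as its limit. A psoriatic plaque can flatten and lose its scale while still red, and that is the state the table does not settle. If raters or centres resolve it differently, the same clinical outcome enters the ISGA response rate as a success in one place and a failure in another.

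The error also need not be balanced. Section 6.1 gives mild pigmentation, described there as including erythema, as the most frequent adverse experience with TC Cream, and the synopsis expects mild red pigmentation. Flat but red lesions may therefore be more common on active treatment than on vehicle. Reading the component lines would count them as successes; reading the headline would count them as failures. The choice of line could then move the comparison in either direction.

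**Working it through.** **1. Plan's own figure.** None applies. Section 9.1 gives 44 per arm without response rates, and this point does not use it.

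**2. Table 6 side by side (paraphrased).**

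| Grade | Erythema in headline | Erythema line | Elevation line | Scaling line |
|---|---|---|---|---|
| 0 | discoloration only if not erythematous | includes diffuse faint pink or red | none | none |
| 1 | faint | up to moderate, ceiling definite red | doubtful (±) | dryness (±) |
| 2 | slight, joined by and/or | same as grade 1 | slight | fine |
| 3 | moderate, joined by and/or | moderate, definite red | moderate | coarser |

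**3. Grade one test lesion.** Take a lesion with elevation as in grade 1 ("possible but difficult to ascertain whether there is a slight elevation above normal skin"), scaling as in grade 1, and definite redness.

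- Component lines: all three grade 1 lines are met. Grade 2 is not, because it needs "slight but definite elevation, typically edges are indistinct or sloped" and fine scale. Result: grade 1.
- Grade 1 headline: redness is definite, not faint. Result: not grade 1.
- Grade 3 headline: with and/or, moderate erythema alone is enough. Result: grade 3.

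**4. Apply the success rules.** Change = baseline grade minus follow-up grade. Section 5.1.1 needs a change of at least 2; section 5.1 also needs a follow-up grade of 0 or 1.

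| Baseline | Lesion called 1 | Lesion called 3 |
|---|---|---|
| 2 | 2 − 1 = 1, failure | 2 − 3 = −1, failure |
| 3 | 3 − 1 = 2, success on both rules | 3 − 3 = 0, failure on both rules |
| 4 | 4 − 1 = 3, success on both rules | 4 − 3 = 1, failure on both rules |
| 5 | 5 − 1 = 4, success on both rules | 5 − 3 = 2, success on 5.1.1, failure on 5.1 |

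A rater who leaves grade 1 because of the headline but stops at grade 2 also records a failure from baseline 3 (3 − 2 = 1). So from baseline 3 any departure from grade 1 reverses the outcome. From baseline 4 on the section 5.1.1 rule, only the grade 3 reading does.

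**5. Does the averaging sentence settle it?** Assume ± is scored 1 and use the score of 3 that Table 2 gives to moderate erythema. The three signs average (1 + 1 + 3)/3 = 1.67. Over five components the average is (5 + BSA score + pruritus score)/5. If each of those two scores runs from 0 to 5, this lies between 5/5 = 1.0 and 15/5 = 3.0. No rounding rule is visible, so the sentence does not decide the grade.

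**6. Grade 0.** A flat, scale-free lesion with faint pink colour fits the grade 0 erythema line but not the grade 0 headline, and fits the faint erythema of the grade 1 headline. From baseline 2, grade 0 is a success (2 − 0 = 2) and grade 1 a failure (2 − 1 = 1).

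**7. Where the conflict stops.** A red lesion with slight but definite elevation and fine scale is not grade 1 on any line. It is grade 2 on the component lines and 3 on the and/or headline, both failures from baseline 3; the difference matters only from baseline 4 on the section 5.1.1 rule. With moderate elevation and coarse scale, every reading gives grade 3. Target lesions use Table 7, where each grade has its own erythema anchor.

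**The case against.** The best defence is that a static global score is a composite. Elevation and scaling rise strictly across grades 1 to 3, so two grades may share an erythema ceiling without error. Read by component lines alone, the test lesion is plainly grade 1. Raters are also blinded (section 3.2), so none can choose the reading by arm. All of this stands, but none of it reconciles the grade 1 headline with its own erythema line or says that the component lines govern. Blinding does not equalise how often the disputed lesion occurs.

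A reader might infer more than the documents support:

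- *The cut is undefined for every definitely red lesion.* It is not; elevation and scaling settle the grade 1 question for the others.
- *The test lesion fits grades 1, 2 and 3 equally.* Grade 2's elevation and scaling lines exclude it, and grade 3 is reached only through the and/or headline.
- *The boundary between grades 1 and 2 is the primary endpoint.* On the section 5.1.1 rule that boundary decides success only from baseline 3, and the ISGA is one of two primary endpoints.
- *The scaling wording also contradicts itself.* This is doubtful: "surface dryness with some white coloration" need not be psoriatic scale.
- *Moderate erythema cannot average 1.* It can: component scores of 3, 1, 1, 0, 0 give 5/5 = 1. Most of the component tables are missing from the public text, so little can rest on this.
- *A loss of power can be quoted.* It cannot. The plan states no response rates, and nothing in it gives the share of patients in the disputed state or how raters would split.

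**Conclusion.** The point holds in a limited form. Two erythema statements in grade 1 of Table 6 conflict, and no precedence rule is visible. For a patient with baseline grade 3 whose lesions end flat or nearly flat, without scale and definitely red, the ISGA outcome depends on which statement the rater uses. A similar conflict in grade 0 affects patients with baseline grade 2 at the cut between 0 and 1.

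The size is unknown: it depends on how many patients end in those states in each arm, which the documents do not give. That the error may differ between arms is an inference from the expected erythema in section 6.1, not a demonstrated bias, and its direction depends on the reading adopted. The conclusion assumes that no removed table or figure contains a precedence rule. It is worth correcting because it touches a primary endpoint and cannot be reliably undone once scores are recorded.

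**What to change.** Before the first subject:

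- Make the headline and the erythema line agree within grade 0 and within grade 1.
- State in Table 6 which line prevails when the signs point to different grades, including how the and/or headlines of grades 2 and 3 are to be read.
- State how the component average is rounded.
- Use that single table for rating and rater training at all centres.

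The anchors do not have to be rewritten to rise strictly, and the faint level need not be the one kept. The sponsor must decide explicitly whether residual redness on a flat lesion counts as disease, bearing in mind that the study drug is itself expected to cause redness. The cost is table wording and training material. The small downside is that the wording may differ slightly from other uses of the scale.

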5.1.2 Target Lesion

Pre-select two target lesions representative of the disease (for example: one from a refractory area, elbow or knee, while the other from the trunk) for separate variables, including induration, erythema, scaling, and BSA on a 6-point score.

Take photographs and measure the severity and extent before the clinical intervention and at every visit.

Effective (average of 2 Target Lesions) = [Baseline (Target Lesions ≥ 2) - Target Lesions

Protocol Version: 00

score at end of treatment] ≥ 2 .

The response to TC Cream will be assessed relative to the placebo group (ratio of patients who achieved the efficacy goal).

Table 7. Severity of Psoriasis Area Severity Index (PASI) at the Target Lesion Site

Score	Grade	Erythema	Scaling	Plaque Elevation
0	Clear	No evidence of erythema	No evidence of scaling	No evidence of plaques above normal skin level
1	Almost Clear	Pink discoloration, minimal erythema	Occasional fine scales hardly noticeable	Slight, just discernable elevation above normal skin level
2	Mild	Light red coloration	Slight but definite roughness, fine scale present, no cracking	Discernable elevation above normal skin level upon examination, but not pronounced
3	Moderate	Moderate redness, but not dark	Moderate roughness, somewhat coarse scaling	Definite plaque formation with rounded/sloped edges to plaque
4	Severe	Dark red coloration	Marked roughness, coarse/thick scaling, cracking may be evident	Marked elevation with hard, distinct edges to plaque
5	Very Severe	Very dark red coloration with induration present	Very thick scales covering extensive area severe cracking/fissures may be evident	Very marked elevation, very hard and sharp edges to plaque

Note: Body Surface Area (BSA) percentage is no longer requested as an individual component sign in the PASI scale, but the BSA percentage and distribution should be recorded at baseline.

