3.3.4 Inclusion Criteria

- Age of 18-70 years old. Both men and women, and members of all races and ethnic groups, will be included
- Consistent with the diagnostic criteria of stable-stage psoriasis vulgaris, and have at least two target lesions suitable for evaluation

Protocol Version: 00

- Women of childbearing age must be using birth control strategies defined by one of the following: 1) a barrier method (condom) and 2) oral contraceptives, during the 8-week study period.
- ISGA score ≥ 2 (at least mild severity)
- BSA (stable stage group): $1\% \leq$ to $\leq 20\%$
- Signed a written informed consent document
- No additional exposure to the sun

Note: Randomized, male-female ratio should be adequately taken into consideration.

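### The target-lesion primary endpoint counts BSA as a scored item in the text but not in its own table, and entry does not require the baseline of 2 that its success rule needs

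*Combined protocol and SAP*

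**What the plan says.** Section 5.1 lists the assessment of target lesions as one of two primary endpoints, beside ISGA. Section 5.1.2 has two representative lesions chosen in advance and graded on separate variables, "including induration, erythema, scaling, and BSA on a 6-point score". It then asks sites to "measure the severity and extent before the clinical intervention and at every visit".

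The scale itself, "Table 7. Severity of Psoriasis Area Severity Index (PASI) at the Target Lesion Site", runs from 0 to 5 and has three sign columns: erythema, scaling and plaque elevation. There is no BSA column. The note beneath it says "Body Surface Area (BSA) percentage is no longer requested as an individual component sign in the PASI scale" and adds that "the BSA percentage and distribution should be recorded at baseline".

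The success rule in 5.1.2 works on the average of the two lesions. It takes a baseline of at least 2, subtracts the end-of-treatment score, and requires a difference of at least 2.

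Section 3.3.4 admits subjects with a global ISGA of at least 2 and BSA between 1% and 20% who "have at least two target lesions suitable for evaluation". It gives no minimum score for those lesions. The ITT set in Section 9.2.3 keeps everyone who was randomized and dispensed medication, with no condition on baseline lesion score.

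**The concern.** There are two gaps in one primary responder definition.

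First, a programmer cannot tell from 5.1.2 whether the lesion score has three items or four. The choice can turn the same patient from a success into a failure. If it is left open, it could be made after the data are unblinded.

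Second, the success rule presupposes a lesion baseline that entry does not secure. For ISGA the two agree: entry and success both start from 2, so every entrant can succeed. For target lesions they do not. A subject who starts too low to fall by 2 is a failure in either arm whatever the treatment does, and the treatment difference is diluted accordingly.

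**Working it through.** **Plan's own figure.** Section 9.1 gives 44 per arm (88 in total) with 90% one-sided power. It states no response rates, effect size or alpha, so the figure cannot be reproduced. The check therefore rests on the scoring rule.

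**Step 1: how the signs are combined.** Section 5.1.2 averages over the two lesions but does not say how the signs within a lesion become one score. Three readings are open:
- a mean of the signs (0-5);
- a single grade per lesion (0-5), using the score column of Table 7;
- a sum (0-15 on three items, 0-20 on four).

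On a sum, 3/3/3 to 3/2/2 goes from 9 to 7, a drop of 2 and a success. On a mean, the same change is 2/3 = 0.67 and a failure. The threshold of 2 therefore has no fixed meaning until the rule is stated.

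**Step 2: effect of BSA, assuming a mean on 0-5.** Take both lesions at 3/3/3 before treatment and 1/1/1 after.
- Three items: (2 + 2 + 2)/3 = 2.0, success.
- Four items, BSA unchanged: (2 + 2 + 2 + 0)/4 = 1.5, failure.
- Four items, BSA down one grade: (2 + 2 + 2 + 1)/4 = 1.75, failure.

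**Step 3: who cannot succeed.** On a 0-5 mean or grade, the largest possible drop equals the baseline. If the two-lesion average is below 2, no outcome reaches 2. Examples on three items:
- Both lesions at erythema 2, scaling 1, elevation 1: baseline 4/3 = 1.33, so the largest drop is 1.33.
- One lesion at 2/2/2 and one at 1/1/2: (2.00 + 1.33)/2 = 1.67.
- Single-grade reading, lesions graded 2 and 1: (2 + 1)/2 = 1.5.

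Nothing in 3.3.4 excludes these lesions. The description of ISGA grade 2 joins the signs with and/or, so one sign at that level can be enough for its opening line.

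**Step 4: what it would cost.** Let f be the share of subjects in each arm who cannot succeed. The documents do not give f, so the values below are assumptions. Both response rates shrink to p(1 - f), and so does their difference. With n = 44 per arm and two-sided 0.05 (the level in Section 9.2.4), the normal approximation for two proportions gives

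power = Φ[(d - 1.96·SE0)/SE1],

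where d is the difference, SE0 the pooled and SE1 the unpooled standard error. I assumed vehicle rates from 5% to 30% and chose the TC rate that gives 90% power at f = 0 (31% against 5%, up to 64% against 30%).

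Worked case, 31% against 5% with f = 20%: the rates become 24.8% and 4.0%, so d = 0.208. SE0 = √(0.144 × 0.856 × 2/44) = 0.0749. SE1 = √((0.248 × 0.752 + 0.04 × 0.96)/44) = 0.0715. Power = Φ(0.857) = 80%.

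| f (assumed) | Power over the assumed rates |
|---|---|
| 0% | 90% |
| 10% | 83-86% |
| 20% | 75-80% |
| 30% | 66-74% |

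At one-sided 0.05, with TC rates again set to give 90% at f = 0, the last three rows become 84-86%, 78-82% and 70-76%.

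**The case against.** The strongest reply is that the score need not be a mean of signs. Section 5.1.2 calls the signs separate variables, its only stated average is over lesions, and Section 5.1 describes outcomes as integer-valued. With one grade per lesion the three-item and four-item contrast does not arise in that form. This stands: Step 2 depends on averaging. It does not rescue the plan, because the missing combination rule is itself part of the gap.

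It can also be said that the Table 7 note concerns PASI, not the target-lesion score, and that it removes a BSA percentage while the text names a 6-point grade. But the table's title places it at the target-lesion site, and it has no BSA column of either kind.

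A reader might infer that no BSA value would exist at Week 8. The documents do not support that: 5.1.2 asks for extent at every visit, and the note asks for a baseline record without ruling out later ones.

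A reader might also infer that a lesion clearing completely from 2/2/2 would be called a failure on four items. That needs the BSA item to stay put in a cleared lesion (6/4 = 1.5). If the item describes lesion extent and falls from 2 to 0, the drop is 8/4 = 2.0 and the lesion succeeds. How BSA is graded cannot be seen in the available text, so the example does not hold.

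The ISGA grades refer to "Majority of lesions have individual scores for induration, erythema, scaling, BSA and Pruritus", and one might extend the criticism to them. A global scale may take in extent and itch by design, and ISGA is a different endpoint, so no change is proposed there. That line, and the requirement that target lesions be representative, make low lesion scores less likely. They do not exclude them, since the line speaks of most lesions rather than the two chosen.

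A rule for counting subjects below 2 would be an alternative to a new entry criterion. It would remove the ambiguity but, if they are counted as failures, not the dilution.

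Finally, Section 5.1 asks for Clear/Almost Clear as well as a 2-grade improvement for all outcomes, while 5.1.2 asks only for the drop. A score going from 4 to 2 is classified both ways. That is a separate inconsistency, and the fix below does not settle it.

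**Conclusion.** The point holds in two parts. Section 5.1.2 contradicts itself on whether BSA is scored, and it leaves the combination of signs undefined. If signs are averaged on 0-5, the same patient moves between a drop of 2.0 (success) and 1.5 or 1.75 (failure). In addition, entry does not guarantee the baseline of 2 that success needs. On a 0-5 mean or grade, any subject whose two-lesion average is below 2 cannot respond yet counts in the ITT denominator.

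A reader might take this second part as bias in favour of one arm. The documents do not support that: under randomization such subjects are expected in both arms, so the cost is a smaller difference and lower power. Nor do the documents show how many there would be. The power figures are illustrations over assumed response rates and assumed shares, not estimates for this trial. On a summed score, the inability to succeed would largely disappear, and a drop of 2 would become a very weak criterion.

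**What to change.** Make three changes before enrolment, or at the latest settle the score definition before unblinding:

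1. In 5.1.2, define the target-lesion score explicitly from the Table 7 signs, including how they combine. For example: the mean of erythema, scaling and plaque elevation over both lesions, at baseline and at Week 8.
2. Delete BSA from the scored components in 5.1.2. Keep it as a separate measure of extent, and state in one place when it is recorded.
3. Add to 3.3.4 a mean baseline target-lesion score of at least 2, computed on that same score.

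The cost is protocol wording and one scoring line on the CRF. The downside is slightly narrower eligibility, because subjects with ISGA of at least 2 but low-scoring target lesions would no longer enter.
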